### **Biomarkers Studies**

- **Material Collected (will be omitted if the same sample is to be collected and stored at the same visit for another protocol, ie IBC registry or 2007-0818):**
- *Pre-treatment: Sonogram-guided core biopsy of tumor mass, CTCs collected in cell search tube, serum, urine.*
- *After completion of 50 Gy (qd) or 45 Gy (bid) and within 15 days of completing treatment the total protocol specified dose to the breast, : sonogram-guided core biopsy, CTCs, serum, urine*
  
- **Proposed Studies:**
- 1. Serum and urine will be collected and stored for future translational studies.
- 2. Multiple cores not greater than 5 will be obtained at the time of each biopsy. Total biopsy number will be at the discretion of the performing physician and studies below will be prioritized in the order they are listed when sufficient material for all is not collected. Paired biopsy specimens (pre and post initiation of therapy) will be treated as follows:
  - Pair 1 and 2: Core material will be delivered fresh to IBC core laboratory. Material will be digested to single cells using established protocols for flow cytometry and/or mammosphere culture 24. Mammosphere efficiency will be correlated to percent stem cell marker expression as well as to residual tumor burden determined pathologically at the time of surgery. Conditioned media from mammosphere cultures may be examined using proteomic analysis for secreted proteins that are selectively regulated after therapy and that are common across patient samples. If material is sufficient, mesenchymal stem cells will be cultured and correlated to CTCs.
  - Pair 3: Microarray analysis will be performed on the entire specimen. Significantly upregulated or down-regulated genes will be correlated to known clinical variables as well as the primary endpoints.

- Pair 4: Material will be transplanted into the cleared mammary fatpads of nod/scid mice to maintain tissue samples and generate new material for additional studies. Tissue fragments from all tumors generated will be frozen.
- Pair 5: Formalin embedded for future biomarker studies. Immunohistochemical analysis for predictive markers related to Capecitabine mechanism (TS, TP, DPT, HNCT1) will be performed post-hoc on these samples and or archived tissue from the primary diagnosis when this core is not collected.

## 7.0 Study Design Discussion

This single arm single institution, open-label, phase II trial will provide sufficient data to define and quantitate the safety and efficacy of the combination of neo-adjuvant concurrent radiation and capecitabine in select locally advanced breast cancer patients.

## 8.0 Selection of Patients

### 1. 8.1 Inclusion Criteria

1. Histological confirmation of invasive breast cancer
2. No contraindications to receiving a course of radiation treatment (pregnancy, prior radiation to the volume with disease, or systemic disease in which radiation therapy is an absolute contraindication).
3. Patients who have chemo-refractory gross disease in the breast causing symptoms (pain, drainage, duress) OR

gross disease in the breast ( $\geq T3$ ) and/or lymph node(s) progressive, persistent, or minimally responsive to chemotherapy deemed inoperable or questionable inoperable  
OR

recurrent gross disease in a previously unirradiated breast or on the chest wall or in the regional lymphatics (core biopsy will not be offered to patients without gross disease in the breast).

4. Are able to swallow and retain oral medication (intact pill).
5. Age over 18.
6. Female gender

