#### **4.2 Radiation Treatment Planning**

Custom immobilization molds (cradle devices) and angle boards are recommended as appropriate per patient body habitus and site of disease. Patients will undergo CT simulation and this will be performed in the treatment position as identified by the attending Radiation Oncologist. Entry primary tumor size based on RECIST criteria will be evaluated on the planning CT obtained for simulation. Treating physician will be asked to enter this data onto a protocol specific form subsequent to the simulation.

When available, cross-sectional and ultrasound diagnostic imaging and reports obtained for clinical use and treatment planning independent of this study will be used to define regions of current and presenting gross disease in the breast and draining lymphatics. These will be contoured on the treatment planning CT. Gross disease at the time of simulation will be labelled gross target volume (GTV), complete radiographic response of prior gross nodal disease not radiographically detectable at the time of radiation planning will be contoured as clinical target volume (CTV). GTV and CTV will receive  $\geq 90\%$  of the protocol-specified dose (50-54 Gy at 2Gy per fraction, 57 Gy at 1.8 Gy per fraction or 51 Gy at 1.5 Gy per fraction bid ). Treatment will be administered with high energy linear accelerators (6-18 MV) as determined by optimized treatment planning techniques. Treatment will be delivered using standard tangential irradiation techniques and these fields will be further optimized by use of cerrobend customized blocks and/or multi-leaf collimators. Dose limiting structures will be contoured and used to limit dose in treatment plans prescribed to  $\geq 60$  Gy (see below).

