### **11.3 Sample Size Considerations and Interim Analyses**

The primary objective of this study is to determine the efficacy of pre-operative radiation with concurrent capecitabine in patients who have experienced a minimal response or progression after standard neoadjuvant chemotherapy. Efficacy will be determined by tumour response (complete response + partial response) as measured by RECIST criteria. Tumour response will be assessed after 45 Gy. Those who do not finish will be considered non-responders. Toxicity will be assessed at the same time. Surgical complications will be assessed independently within 6 weeks of surgery. Only grade three toxicity will be considered in the stopping rules. This study will be monitored for both efficacy and safety. Safety will be determined by the rate of grade 3 or higher toxicities, excluding acute skin toxicity. This regimen will not be considered of interest for further study if there is a high probability that the response rate is less than 80% or the severe toxicity rate is greater than 20%. Priors regarding response are based on combined retrospective data from three studies of 135 total patients treated for gross disease in the breast at our institution and detailed in the background (sections 3.2 and 3.5). Local control (a surrogate for response) at 5-years in patients treated for gross IBC disease in the breast with radiation alone was 75% (N = 42, unpublished). In 38 similar patients with non-inflammatory breast cancer local control was 70% at 5 years. In an unpublished retrospective analysis of 55 patients treated with the regimen proposed herein, 5-year local control was 85% (Perkins, SABCS abstract, 2007). There are limited and poor data regarding radiation alone toxicity in this exact cohort. The priors for toxicity were based on aggressive xrt in post-mastectomy patients (N = 192). In these patients, we expect a 15% rate of Grade 3 toxicities in patients receiving 60Gy and a 29% rate of Grade 3 toxicities in patients receiving 66Gy, and unpublished data. Clinically we are currently limiting the use of the latter regimen based on the impression that this is unacceptably high toxicity, so we are targeting a Grade 3 toxicity rate of no more than 20%. All patients who receive any treatment will be included in the analyses of both efficacy and safety. Patients who are not evaluable for response will be considered non-responders. The final analysis will be an Intent to Treat analysis. A total of 60 patients will be enrolled at the rate of 3-4 patients per month. Stopping boundaries will be assessed in cohorts of 5 patients after a minimum of 10 patients have been enrolled. Response and toxicity will be monitored independently. The method of Thall and Simon will be employed to perform interim monitoring.

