##### **11.6.1 Primary Analysis**

The primary endpoint in this study is response defined as the percentage of subjects achieving a complete or partial tumor response using RECIST criteria. The response rate will be calculated from the view of best response that records confirmed cases of CR or PR. Subjects with unknown or missing response will be treated as non-responders; i.e., they will be included in the denominator when calculating the percentage. Response will be evaluated by the recist criteria 4 weeks (+/- 4 days) after completion of radiation therapy.

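### Entry does not require a RECIST-measurable lesion, yet the primary endpoint is RECIST response with non-evaluable patients scored as failures; unless Appendix F covers them, such patients count against the regimen whatever its effect.

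*Combined protocol and SAP*

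**What the plan says.** **Eligibility (Section 8.1).** There are three alternative routes in, all worded in terms of gross disease:

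- symptomatic breast disease: "Patients who have chemo-refractory gross disease in the breast causing symptoms"
- breast disease of at least T3 and/or nodal disease, "progressive, persistent, or minimally responsive to chemotherapy deemed inoperable or questionable inoperable"
- recurrence: "recurrent gross disease in a previously unirradiated breast or on the chest wall or in the regional lymphatics"

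None sets a RECIST-measurability condition or a minimum lesion diameter. Section 8.2 excludes nobody on that ground.

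**Baseline measurement.** Section 4.2 says: "Entry primary tumor size based on RECIST criteria will be evaluated on the planning CT obtained for simulation". Section 6.0 is broader: breast and nodal lesions are sized from the initial clinical examination as well as the planning CT. Neither section says what happens when nothing is measurable, and neither names chest-wall lesions.

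**Endpoint and scoring.** Section 11.3: "Efficacy will be determined by tumour response (complete response + partial response) as measured by RECIST criteria". For patients who cannot be assessed, the same section says "Patients who are not evaluable for response will be considered non-responders", and Section 11.6.1 says "Subjects with unknown or missing response will be treated as non-responders". Sections 1.0, 11.3 and 11.5 make the denominator every treated patient. Section 9.2 does not replace patients who come off treatment or off study. Section 11.6.2 has an evaluable-only response rate, as a secondary analysis.

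**Use of the result.** The response count is compared with a futility boundary every 5 patients from the tenth (Sections 11.3 and 11.3.1). Section 11.1 sets the final criterion: response of at least 80% and grade III toxicity, excluding acute skin toxicity, below 20%.

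**The concern.** A partial response by RECIST is a reduction in measured diameters. A patient with no measurable lesion at baseline, for example with diffuse inflammatory or chest-wall disease, has no diameter in which to show one. Under the scoring rules as printed she is a non-responder on the day she enrols, and that failure says nothing about radiation with capecitabine.

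Two decisions use the diluted rate. The interim futility rule could stop a regimen that meets its target in the patients who can be measured, and the final estimate is compared with 80% in a denominator that includes patients who could not respond by definition. The operating characteristics in Section 11.3.3 make no allowance for such patients.

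**Working it through.** **Inputs.** From Section 11.3.1: priors beta(1.6, 0.4) for response and beta(0.4, 1.6) for toxicity on the study regimen, beta(80, 20) and beta(20, 80) for the targets, cut-offs 0.95 and 0.925, and the boundary table. From Section 11.3: maximum 60 patients, looks every 5 from 10, response and toxicity monitored independently. From Section 11.1: the 80% and 20% limits. The share f without measurable disease is **not in the documents** and is assumed.

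**Step 1: reproduce the plan.** Numerical integration of the two posterior probabilities returns all 11 response and all 11 toxicity boundaries exactly. An exact binomial recursion over the looks at 10, 15, …, 55 (a crossing at 60 is not early) gives early stopping of 0.084 and an average of 56.7 patients at response 0.80 and toxicity 0.10. Section 11.3.3 prints 0.08 and 56.7. The other eight rows also agree within tolerance. The printed figures are right for a trial in which the stated response probability applies to every patient counted.

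**Step 2: add non-measurable patients.** If a share f is always scored as non-response and measurable patients respond with probability p, the probability that a patient counts as a response is

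p_obs = p × (1 − f).

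For p = 0.80: f = 5% gives 0.80 × 0.95 = 0.76, and f = 10% gives 0.80 × 0.90 = 0.72.

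**Step 3: chance of meeting the final criterion.** With 60 patients, 80% is 48 responses. Toxicity below 20% means at most 11 events, since 12/60 is exactly 20%. With independent monitoring,

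P(criterion) = P(no response stop and ≥ 48 responses) × P(no toxicity stop and ≤ 11 toxicities).

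At toxicity 0.10 the second factor is 0.983. For p = 0.80 and f = 0, 5%, 10% the products are 0.569 × 0.983 = 0.56, 0.284 × 0.983 = 0.28 and 0.104 × 0.983 = 0.10.

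**Results, toxicity 0.10**

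| True response in measurable patients | Assumed share f | Rate as counted | Early stop | Average N | P(criterion) |
|---|---|---|---|---|---|
| 0.80 | 0 | 0.80 | 0.084 | 56.7 | 0.56 |
| 0.80 | 5% | 0.76 | 0.210 | 52.5 | 0.28 |
| 0.80 | 10% | 0.72 | 0.412 | 45.9 | 0.10 |
| 0.80 | 15% | 0.68 | 0.640 | 37.8 | 0.03 |
| 0.90 | 0 | 0.90 | 0.005 | 59.7 | 0.98 |
| 0.90 | 5% | 0.855 | 0.017 | 59.2 | 0.89 |
| 0.90 | 10% | 0.81 | 0.064 | 57.4 | 0.63 |

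At a true rate of 0.85, early stopping is 0.020, 0.068 and 0.190 for shares of 0, 5% and 10%.

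**A direct reading.** Three non-measurable patients in 60 (5%) mean that 48 responses must come from 57 patients, or 84.2%. Six (10%) mean 48 from 54, or 88.9%. Twelve (20%) mean 48 from 48.

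**The case against.** **Appendix F may settle it.** Response is defined by reference to that appendix, and the baseline form is Appendix G; neither was available for this review. Appendix F could define baseline measurability or give non-measurable disease a response category. Nor does any available section equate non-evaluable with non-measurable at entry. This stands, and it makes the point conditional. It need not remove it. If, as an assumption, non-measurable patients were credited with complete response at the 33% clinical rate reported in Section 3.5, a 10% share would give p_obs = 0.80 × 0.90 + 0.33 × 0.10 = 0.753, early stopping of 0.24 and a criterion chance of 0.24.

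**The entry gap is narrow.** Every route requires gross disease, drainage is a symptom attached to that disease and not a form of it, the inoperable-breast route adds T3 or more, and Section 6.0 allows sizing by examination. This is fair, and it may keep the share small. But Section 3.1 notes that inflammatory disease is classed T4d, so T3 or more can be met by category and not by diameter.

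**The denominator is deliberate.** Counting every treated patient and scoring unknown response as failure is a standard conservative choice. That holds for dropout and missing follow-up. It is less apt where the outcome could not have been measured from the start. The evaluable-only rate in Section 11.6.2 helps final interpretation, but it does not feed the boundaries and cannot undo an early stop.

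**80% is the most sensitive case.** A true rate equal to the target is where dilution costs most. This stands, so the 90% results are shown beside it.

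**Conclusion.** The gap is real: the eligibility criteria set no measurability condition, and the scoring rules convert lack of evaluability into failure at the interim looks and at the end. Unless Appendix F provides otherwise, patients without a measurable baseline lesion are counted as failures regardless of treatment effect.

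The size depends on two quantities that the plan does not give: the share of such patients and the true response rate in the others. Near the 80% target, a 5% to 10% share moves early stopping from 0.08 to 0.21–0.41. At 90% it stays at 0.02–0.06, although a 10% share still cuts the chance of meeting the criterion from 0.98 to 0.63.

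A reader might infer three stronger things, which the documents do not support:

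- that these patients must be non-responders: this turns on Appendix F;
- that the share is large because the trial targets inflammatory cancer: Section 2.0 describes a broad group with and without it, and Section 11.3.3 treats it as a subgroup;
- that a false futility stop is likely: that needs both a material share and a true rate close to the target.

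The repair is cheap and uses assessments already planned, so it should be made.

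**What to change.** Check Appendix F first. If it does not settle how these patients are scored, choose one of the following.

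1. **Entry condition.** Add to Section 8.1 at least one RECIST-measurable lesion at baseline, on the planning CT or by the clinical examination already recorded under Section 6.0. The existing boundaries and Section 11.3.3 then apply as printed. The cost is a slightly narrower entry population.
2. **Response denominator.** Leave entry as it is, but count response, interim and final, only in treated patients with such a lesion. Apply the response boundaries by the number of those patients, amend Sections 1.0, 11.3, 11.5 and 11.6.1 to match, and restate Section 11.3.3, because response and toxicity counts would then differ at each look. The cost is that recalculation and a few treated patients not counted for response.

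Under option 2 the set is fixed by baseline findings, so it introduces no selection on post-treatment outcome. Under either option, keep all treated patients for toxicity and keep the non-responder rule for missing follow-up. Report the all-treated response rate as a sensitivity analysis.

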### 8.2 Exclusion Criteria

1. Have an active or uncontrolled infection.
2. Have dementia, altered mental status, or any psychiatric condition that would prohibit the understanding or rendering of informed consent.
3. Have used an investigational drug within 21 days preceding the first dose of study medication.
4. Are receiving therapeutic anti-coagulation therapy (i.e. warfarin, heparin).
5. Uncontrolled arrhythmia or history of CHF based on clinical history or physical exam.
6. Patient cannot receive whole brain irradiation concurrently with Xeloda treatment.

## 9.0 Withdrawal Criteria

### 9.0 Withdrawal Criteria

A subject may voluntarily discontinue participation in this study at any time. The investigator may also, at his or her discretion, discontinue the subject from participating in this study at any time. In addition, study medication will be discontinued if unmanageable toxicity is documented, or the subject becomes pregnant.

If the subject is discontinued from participation in the study for any reason, the investigator must make every effort to perform the evaluations as shown under 'Withdrawal' in the respective Time and Events Table (Appendix E).

A subject will also be taken off study treatment if any of the following occur:

#### 9.1 During Radiation Treatment:

1. Locoregional disease progression.
2. Treatment is interrupted for more than 1 consecutive week.
3. An intercurrent illness, which would in the judgment of the Study Investigator, affect assessments of clinical status to a significant degree or require discontinuation of study treatment.
4. Nonprotocol therapy (chemotherapy) is administered during study treatment.
5. Non-compliance with protocol or treatment.
6. Refuses to continue treatment. Subject will undergo surgery; toxicity data will continue to be collected.

#### 9.2 Subjects will be considered off study if any of the following occur:

1. Withdrawal of consent (subject will not be contacted and no further information will be collected).
2. Death.

Subjects who are taken off study treatment or who are considered to be off study will not be replaced.

## 10.0 Endpoints

### Primary

- Response evaluated by RECIST criteria (APPENDIX F)

### i. Secondary

The secondary efficacy objectives of the study are:

- To determine the rate of conversion to operable and cCR and pCR after completion

of all protocol specified therapy among patients who go on to surgery. This includes the following:

- Pre-operative concurrent radiation with capecitabine to the breast and at risk or involved regional lymph node basins
- To determine locoregional control of unresected nodal disease treated to definitive radiation dose ( $\geq 60$  Gy)

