#### i. Efficacy

The secondary efficacy objectives of the study are:

- To determine the rate of conversion to operable, cCR, and pCR after completion of all protocol specified therapy. This includes the following:
  - Pre-operative concurrent radiation with capecitabine to the breast and at risk or involved regional lymph node basins
- To determine locoregional control of unresected nodal disease treated to definitive radiation dose ( $\geq 60\text{Gy}$ )

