#### **11.5 Analysis Populations**

Analyses of both efficacy and safety will be performed in the intent-to-treat (ITT) population, and will comprise all patients who received at least one dose of the investigational product. The surgical population includes only subjects who underwent definitive surgery.

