#### **11.6 Efficacy Analysis**

The ITT population will be used for the primary analysis of both the efficacy and safety data. The surgical population will be used for a secondary analysis of the surgical efficacy data. Only patients who undergo both pre-treatment and post-treatment core biopsies will be considered in the primary translational analysis.

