##### **11.6.2 Secondary Analysis**

Patients who were deemed at time of enrolment to be inoperable or questionably inoperable (requiring flap closure with doubt regarding ability to obtain negative margins based on surgical oncology assessment) who have objective clinical response and receive mastectomy or are offered mastectomy but refuse will be considered having converted to operable. Patients who are resectable but considered inoperable based on advanced locoregional disease or M1 disease who have a mastectomy and no FDG-avid disease on PET at 3 month follow up will also be considered having converted to operable.

A secondary indicator of treatment efficacy is pCR. pCR is defined as the lack of any invasive disease in the breast and lymph nodes. A pathologist at the University of Texas M.D. Anderson Cancer Center will perform accurate sampling and review of all cases that have surgery. pCR will be assessed at the time of surgery following the completion of all protocol specified neoadjuvant chemotherapy, which will be approximately 26

weeks following the start of neoadjuvant chemotherapy. Subjects with unknown or missing response and those who do not convert to operable will be included in the primary efficacy analysis as non-responders.

A secondary analysis will calculate response rate based on subjects with evaluable tumor response only; i.e., the denominator will only include subjects with CR, PR, SD, or PD and will not include those with unknown or missing best response.

Exact 95% confidence limits for the clinical response rate will be calculated.

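### Section 10.0, read literally, limits conversion to operable and cCR (as well as pCR) to patients who reach surgery, against the conversion rule in Section 11.6.2; a minor second point is that locoregional control is defined at ≥ 60 Gy but scored only above 60 Gy.

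*Combined protocol and SAP*

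**What the plan says.** **Conversion, cCR and pCR.** Section 1.0 (i. Efficacy) sets the objective as "To determine the rate of conversion to operable, cCR, and pCR after completion of all protocol specified therapy", with no mention of surgery. Section 10.0 (i. Secondary) repeats it but adds the limit "of all protocol specified therapy among patients who go on to surgery". In both places a sub-bullet refers to pre-operative treatment, whereas the primary objective covers pre-operative or palliative treatment.

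Section 11.6.2 gives the working definition of conversion, by two routes. The first starts from "Patients who were deemed at time of enrolment to be inoperable or questionably inoperable" and says that those "who have objective clinical response and receive mastectomy or are offered mastectomy but refuse will be considered having converted to operable". The second concerns patients considered inoperable because of "advanced locoregional disease or M1 disease who have a mastectomy and no FDG-avid disease on PET at 3 month follow up".

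On populations, Section 11.3 says "All patients who receive any treatment will be included in the analyses of both efficacy and safety". Section 11.5 says "Analyses of both efficacy and safety will be performed in the intent-to-treat (ITT) population" and then defines a separate surgical population. Section 11.6 adds "The surgical population will be used for a secondary analysis of the surgical efficacy data", without naming the outcomes meant.

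**Locoregional control.** Sections 1.0 and 10.0 define this endpoint for unresected nodal disease treated to at least 60 Gy. The scoring rule in Section 6.0 covers fields and sites that receive more than 60 Gy. Section 4.1 permits total doses that start at 60 Gy.

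**The concern.** Conversion asks what share of patients who could not be operated on became operable. If only operated patients are counted, most of the definition is met by being in the denominator, and the failures are missing from it. Patients who declined an offered mastectomy, whom Section 11.6.2 counts as successes, drop out as well. cCR needs no operation, so making it conditional on later surgery selects on something that happens after treatment.

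Two analysts could therefore report different conversion and cCR rates from the same data, and the choice could be made after the results are known. Conversion is one of the purposes that Section 2.0 gives for this treatment.

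For locoregional control, a site at exactly 60 Gy belongs to the endpoint but falls under no scoring rule.

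**Working it through.** **1. The plan's own figures.** The plan gives no target or precision for conversion, cCR, pCR or locoregional control. Its final-analysis interval for primary response reproduces: 54 responses in 60 with a Beta(1.6, 0.4) prior gives Beta(55.6, 6.4), with 95% limits 81.06% and 95.89% (stated: 81.1% and 95.9%). That interval uses all 60 patients and is untouched by this point. The background rates also reproduce: 32/38 = 84.2% (Section 3.2, stated 84%) and 23/28 = 82.1% (Section 3.5, stated 82%). Both use the whole inoperable group as denominator.

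**2. The texts side by side, for conversion.**

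| Patient | Section 10.0, read literally | Section 11.6.2 |
|---|---|---|
| Operated, meets the response or PET condition | counted, converted | counted, converted |
| Responds, is offered mastectomy, declines | not counted | converted (first route) |
| Stays inoperable | not counted | in the starting group, not converted |

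**3. Size for conversion.** Among patients in the Section 11.6.2 starting group, let f be the share operated, r the share of operated patients who meet the conversion condition, and q the share of non-operated patients who are converted refusers.

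- Surgery-only rate = r
- Rate in the whole group = f·r + (1 − f)·q
- Excess = r − f·r − (1 − f)·q = (1 − f)(r − q)

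Inputs for f: 32/38 = 0.842; 23/28 = 0.821; 50/55 = 0.909. The last takes the 91% converted in the 55-patient series (Section 3.5) as a proxy for operated, because the number operated is not given. The values of r and q are assumptions.

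| r, q (assumed) | f = 32/38 | f = 23/28 | f = 50/55 |
|---|---|---|---|
| 1, 0 | 15.8 | 17.9 | 9.1 |
| 0.8, 0 | 12.6 | 14.3 | 7.3 |
| 0.8, 0.25 | 8.7 | 9.8 | 5.0 |
| 0.6, 0.5 | 1.6 | 1.8 | 0.9 |
| 0.8, 1 | −3.2 | −3.6 | −1.8 |

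Entries are percentage points. In the 28-patient series all 5 non-operated patients had progressed, so q = 0 there, and the excess is 10.7 to 17.9 points for r from 0.6 to 1.

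**4. cCR.** The direction is not known. If the 33% in the 55-patient series is of all 55 (18 patients) and 50 were operated, the rate is 18/55 = 32.7% overall. Among those operated it is 18/50 = 36.0% if no non-operated patient had cCR, and 13/50 = 26.0% if all 5 did. The shift is then +3.3 to −6.7 points.

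**5. Locoregional control.** Exactly 60 Gy is reachable in whole fractions under two of the three listed regimens: 50/2 + 10/2 = 30 fractions, and 51/1.5 + 9/1.5 = 40 fractions. The number of such sites is unknown and may be zero. Separately, the score list in Section 6.0 appears to put no response and progression in one category, and no section supplied says which scores count as control.

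**The case against.** The best reply is that the qualifier is simply misplaced and was meant for pCR alone. That is plausible. In Section 1.0 a surgery limit sits on wound complications and not on efficacy; in Section 10.0 it is missing from wound complications and appears on efficacy. An analyst would probably follow the detailed rule in Section 11.6.2. This lowers the risk, but the endpoint section still contradicts the analysis section, and one edit removes the contradiction.

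Several stronger readings are tempting, and the documents do not support them:

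- *That a surgery-only pCR analysis breaks the plan.* pCR is assessed at surgery, and Sections 11.5 and 11.6 provide a surgical population for a secondary analysis. The Section 11.3 sentence on all treated patients mainly concerns primary response and monitoring.
- *That cCR and pCR must be reported on all treated patients.* The pre-operative sub-bullet in Sections 1.0 and 10.0 leaves room for a pre-operative-intent population, so this is a choice of estimand.
- *That the background data show how far pCR would move.* Section 3.5 does not give the denominator of its 20% pCR rate, so no difference can be derived.
- *That Section 11.6.2 sets the conversion denominator by keeping non-converters as non-responders.* That sentence sits in the pCR paragraph and refers to the primary efficacy analysis, so its target is unclear.
- *That only stable sites make the control rate ambiguous.* With no stated rule for control, partial responses are open too.

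It is also fair to say that the merged score may be garbled text, and that the RECIST appendix and the forms, which are not in the text supplied, may separate the two categories.

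**Conclusion.** The contradiction is real and should be corrected. It is clearest for conversion, where Section 10.0 excludes refusers whom Section 11.6.2 counts as converted, and also excludes patients who remain inoperable. It holds for cCR, which does not depend on surgery. It does not extend to a surgical-population pCR analysis.

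For conversion, a surgery-only rate would be about 9 to 18 points too high if f is 0.82 to 0.91, r = 1 and q = 0. The excess shrinks as q rises and reverses if q exceeds r. This is an illustration: r and q are assumed, one f is a proxy, and the series do not bound this trial, which also enrols palliative and oligometastatic patients.

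The 60 Gy mismatch is a true inconsistency but a minor one. The primary RECIST analysis, the sample size and the stopping boundaries are unaffected.

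**What to change.** **Conversion and cCR**

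- Remove the surgery restriction from conversion and cCR in Section 10.0, and align Sections 1.0, 10.0, 11.6 and 11.6.2.
- For conversion, use all treated patients classed at enrolment as inoperable or questionably inoperable under Section 11.6.2, including those considered inoperable for advanced locoregional or M1 disease. Keep that class even if the recorded intent later changes to palliative, as Section 6.0 allows. Put refusers in both numerator and denominator.
- For cCR, use a denominator fixed at enrolment and not conditional on later surgery: all treated patients, or all treated with pre-operative intent. State which.
- Keep the surgical-population pCR analysis if wanted, and say in Section 11.6 which outcomes are surgical efficacy data.

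**Locoregional control (minor)**

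- Reconcile the analysis threshold across Sections 1.0, 6.0 and 10.0, so that every site in the endpoint is scored.
- State in Section 11 which scores count as control. If the forms do not already do so, score stable and progressive disease separately.

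**Cost.** Wording in Sections 1, 6, 10 and 11, and at most one extra score category at visits already planned. Whether the forms already capture this, or the operability class at enrolment, cannot be seen from the text supplied. The downside is that the reported conversion rate will probably be less favourable. The change should be made before outcome data are reviewed.
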